## 5.2. Exclusion Criteria

Any potential participant who meets any of the following criteria will be excluded from participating in the study:

1. Had previous exposure to BDQ.
2. Has active TB disease.
3. Has cystic fibrosis, medically unstable respiratory disease (eg, COPD, bronchiectasis, asthma).  
  
Note: Medically unstable respiratory disease is defined as their symptom/sign are not controlled with medication for their respiratory disease and exacerbation was observed within 6 months prior to screening.
4. Has one or more cavities  $\geq 2$  cm in diameter on a chest CT scan taken within 6 months prior to screening or at screening.
5. Criterion modified per Amendment 8.
- 5.1 Treatment already includes an injectable/inhaled aminoglycoside within 3 months prior to screening or the investigator deems the participant to be a candidate for an injectable/inhaled aminoglycoside during screening period or at Day 1.
6. Criterion modified per Amendment 8.
- 6.1 Has a history of documented macrolide-resistant MAC strain within 24 months prior to screening or at screening. For CAM, MIC of  $\geq 32$   $\mu\text{g/mL}$  indicates resistance according to the Clinical and Laboratory Standards Institute [CLSI] M24 guidelines.

Note: In case a subject has  $\geq 2$  documented DST results within 24 months prior to screening, the subject is eligible if the latest result is susceptible and DST at screening is confirmed susceptible.

7. Has a history of a myocardial infarction, or a presence of any clinically significant cardiac disease, as determined by the investigator.
8. Has experienced one or more of the following risk factors for QT prolongation:
  - personal or family history of Long QT Syndrome
  - personal history of cardiac disease, symptomatic or asymptomatic arrhythmias, with the exception of sinus arrhythmia
  - a confirmed prolongation of the QT or QT interval corrected according to QTcF  $\geq 450$  milliseconds (ms) in the screening ECG (retesting to reassess eligibility will be allowed once using an unscheduled visit during the screening period)
  - pathologic Q-waves (defined as Q-wave  $> 40$  ms or depth  $> 0.4$ - $0.5$  mV)
  - evidence of ventricular pre-excitation (eg, Wolff Parkinson White syndrome)
  - electrocardiographic evidence of complete or clinically significant incomplete left bundle branch block or right bundle branch block
  - evidence of second- or third-degree heart block
  - intraventricular conduction delay with QRS duration  $> 120$  ms
  - bradycardia as defined by sinus rate less than 50 beats per minute
  - syncope (ie, cardiac syncope not including syncope due to vasovagal or epileptic causes)
  - risk factors for Torsades de Pointes (eg, heart failure, hypokalemia, or hypomagnesemia)
9. Has a relevant history or current condition that might interfere with drug absorption, distribution, metabolism, or excretion such as malabsorption syndrome or renal, or hepatic disease.
10. Has active malignancy (primary or metastatic) or any other malignancy requiring chemotherapy or radiotherapy within 1 year before screening (exceptions are squamous and basal cell carcinomas of the skin and carcinoma in situ of the cervix, or malignancy, which is considered cured with minimal risk of recurrence).
11. Has known allergies, hypersensitivity, or intolerance to BDQ, CAM, EB, RFP or RBT (refer to IB and addendum of BDQ, and package insert of each drug).
12. Has the following toxicities during the screening period:
  - Serum creatinine is  $> 1.5 \times$  upper limit of normal (ULN)

- Aspartate aminotransferase (AST) is  $>3.0 \times \text{ULN}$
  - Alanine aminotransferase (ALT) is  $>3.0 \times \text{ULN}$
  - Alkaline phosphatase (ALP) is  $>3.0 \times \text{ULN}$
  - Total bilirubin is  $>2.0 \times \text{ULN}$  or  $>1.5 \times \text{ULN}$  when accompanied by any increase over ULN in other liver function test
13. Has a history of HIV antibody positive, tests positive for HIV at screening, a history of hepatitis B surface antigen (HBsAg), or hepatitis C antibody (anti-HCV) positive, or other clinically active liver disease, or tests positive for HBsAg or anti-HCV at screening. A participant who has completed treatment for hepatitis C and has been cured is eligible.
  14. Has a history of drug or alcohol abuse that, in the investigator's opinion, would compromise the participant's safety or compliance to the study protocol procedures.
  15. Criterion modified per Amendment 8.
  - 15.1 Has contraindications to the use of CAM, EB, RFP or RBT per local prescribing information in Japan, South Korea or Taiwan.
  16. Has taken any prohibited therapies as noted in Section 6.8, [Concomitant Therapy](#) before the planned first dose of study intervention.
  17. Received an investigational study intervention or used an invasive investigational medical device within 60 days before the planned first dose of study intervention or is currently enrolled in an investigational study.
  18. Is pregnant, or breast-feeding, while enrolled in this study or within 90 days after the last dose of study intervention.
  19. Plans to father a child while enrolled in this study or within 90 days after the last dose of study intervention or who is unwilling to use acceptable methods of contraception as outlined in Section 10.5, [Appendix 5: Contraceptive Guidance](#).
  20. Has any condition for which, in the opinion of the investigator, participation would not be in the best interest of the participant (eg, compromise the well-being) or that could prevent, limit, or confound the protocol-specified assessments.
  21. Has preplanned surgery or procedures that would interfere with the conduct of the study.  
  
Note: Participants with planned surgical procedures to be conducted under local anesthesia may participate.
  22. Employee of the investigator or study site, with direct involvement in the proposed study or other studies under the direction of that investigator or study site, as well as family members of the employees or the investigator.

23. Is co-infected with NTM species other than MAC on sputum culture at screening.

Note: If both MAC and NTM species other than MAC were detected on screening sputum culture, and previous test result(s) suggested possible contamination such as NTM species other than MAC was not detected before screening, a retesting of screening sputum culture (repeat of sputum collection and sputum culture) will be allowed once. The time required for retesting will not be included in the duration of the screening period (9 weeks).

**NOTE:** Investigators should ensure that all study enrollment criteria have been met at screening and at baseline (Day 1). If a participant's clinical status changes (including any available laboratory results or receipt of additional medical records) after screening but before the first dose of study intervention is given such that he or she no longer meets all eligibility criteria, then the participant should be excluded from participation in the study.

**NOTE:** Retesting of abnormal laboratory, ECG and physical examination values that may lead to exclusion will be allowed once. Retesting will take place during an unscheduled visit in the screening period. If the repeat test meets the study enrollment criteria, the participant can be included in the study.

**NOTE:** If a subject is excluded due to COVID-19 related circumstances during the screening period, the reason for screen failure should be recorded as exclusion criterion number 25 on the eCRF (refer to COVID-19 Appendix).

### 5.3. Lifestyle Considerations

Potential participants must be willing and able to adhere to the following lifestyle restrictions during the course of the study to be eligible for participation:

1. Refer to Section 6.8, [Concomitant Therapy](#) for details regarding prohibited therapy during the study.
2. Agree to follow all requirements that must be met during the study as noted in the Inclusion and Exclusion Criteria (eg, contraceptive requirements).

#### 5.3.1. Activity

1. Participants will abstain from strenuous exercise for 24 hours before each blood collection for clinical laboratory tests. Participants may participate in light recreational activities during studies (eg, watching television, reading).
2. Strenuous exercise may affect study specified assessments and safety laboratory results; for this reason, strenuous exercise should be avoided within 24 hours before all planned study visits and during stays in the study site.
3. Avoid donating blood for at least 30 days after last dose of BDQ of the study.

## **5.4. Screen Failures**

### **Participant Identification, Enrollment, and Screening Logs**

The investigator agrees to complete a participant identification and enrollment log to permit easy identification of each participant during and after the study. This document will be reviewed by the sponsor study-site contact for completeness.

The participant identification and enrollment log will be treated as confidential and will be filed by the investigator in the study file. To ensure participant confidentiality, no copy will be made. All reports and communications relating to the study will identify participants by participant identification and age at initial informed consent. In cases where the participant is not randomized into the study, the date seen and age at initial informed consent will be used.

Individuals who do not meet the criteria for participation in this study (screen failure) may be rescreened, including candidates whose microbiological testing at screening is not eligible, such as culture negative, resistance to CAM, etc. Rescreened participants should be assigned a different participant number with the initial screening.

## **5.5. Criteria for Temporarily Delaying Enrollment/Randomization/Administration of Study Intervention**

Not applicable.

## **6. STUDY INTERVENTION AND CONCOMITANT THERAPY**

### **6.1. Study Interventions Administered**

The study drug BDQ and the comparator rifamycin (RFP and RBT) will be provided as tablets for oral administration. BDQ will be taken with food in the morning at approximately the same time each day, depending on visit and visit assessments. Rifamycin (RFP or RBT) will be taken according to the investigator's instructions. Combination drugs will not be provided by the sponsor and marketed product at study sites should be administered. Participants will be instructed to take their assigned dose of the study intervention or comparator and combination drugs, per [Table 2](#).

**Table 2: Dosage and Administration Table for Study Interventions and Combination Drugs**

Group	Group A	Group B		Group A and Group B	
Intervention Name	BDQ (TMC207) a,b	Rifamycin a,b,c		clarithromycin (CAM)	ethambutol (EB)
		rifampicin (RFP)	rifabutin (RBT)		
Category	Study Interventions (Investigational Medicinal Product)			Non-Investigational Medicinal Product	
	Study drug	Comparator		Combination drugs	
Formulation and strengths	100 mg tablet	150 mg capsule	150 mg capsule	200 or 250 mg tablet	125, 250, 400 or 800 mg tablet
Dosage level(s)	JP, SK, TW: Loading phase (Week 1-2): 400 mg qd, Maintenance phase (Week 3-48): 200 mg biw with at least 72 hours between doses	JP, SK, TW: 450 mg qd, Maximum daily dose 600 mg	JP: 300 mg qd SK, TW: 150 or 300 mg qd	JP: 800 mg/day d (400 mg bid) SK, TW: 1,000 mg/day d (500 mg bid)	JP: 500-750 mg qd, Maximum daily dose 1.0 g SK, TW: 15 mg/kg e qd
Route of administration	Oral	Oral	Oral	Oral	Oral
Sourcing	Provided centrally by the sponsor			Provided locally by the trial site	
a Participants who are taking rifamycin before start of treatment with BDQ will be required to discontinue rifamycin to allow for a minimum 14-day washout period to avoid DDIs between rifamycin and BDQ. b Bedaquiline and rifamycin (RFP/RBT) will be provided under the responsibility of the sponsor. c RFP is basically administered in all countries, but RBT will be considered if RFP is ineffective or cannot be used in Japan or at the discretion of the investigator in South Korea and Taiwan. The dose of RBT is based on the recommended dose in each country; 300 mg/day in Japan, and 300 mg/day for ≥50 kg and 150 mg/day for <50 kg in South Korea and Taiwan. d Daily dose of CAM on Day 1 is 800 mg (400 mg bid) in Japan and 1,000 mg (500 mg bid) in South Korea and Taiwan. If a dose reduction is required due to AEs after the start of treatment, the daily dose of CAM may be reduced to 750 mg (South Korea and Taiwan) or 600 mg (Japan) at the discretion of the investigator. e Based on 15 mg/kg, the daily dose will be determined at the discretion of the investigator.					
Key: JP=Japan; SK=South Korea; TW=Taiwan; AE=adverse event; BDQ=bedaquiline; bid: bis in die (twice a day), biw: bis in week (twice a week); qd: quaque die (once a day), CAM=clarithromycin; EB=ethambutol; RBT=rifabutin; RFP=rifampicin; DDI= drug-drug interactions					

Study intervention administration must be captured in the source documents and the electronic case report form (eCRF).

BDQ will be manufactured and provided under the responsibility of the sponsor. Refer to the IB for a list of excipients of BDQ. Rifamycin (RFP or RBT) will be provided under the responsibility of the sponsor. Refer to the respective Japanese package insert for a list of excipients of Rifamycin (RFP or RBT).

For a definition of study intervention overdose, refer to Section 6.7, [Treatment of Overdose](#).

## 6.2. Preparation/Handling/Storage/Accountability

### Preparation/Handling/Storage

All study intervention must be stored in the original blister sheet or container within the designated temperature range indicated by label of the kit in order to protect from light.

Refer to the pharmacy manual/study intervention and procedures manual for additional guidance on study intervention preparation, handling, and storage.

Preparation, handling, and storage of combination drugs (CAM and EB) will be in accordance with procedures of the study sites.

### **Accountability**

The investigator is responsible for ensuring that all study intervention received at the site is inventoried and accounted for throughout the study. The dispensing of study intervention to the participant and the return of study intervention from the participant must be documented on the study intervention accountability form. Participants must be instructed to return all original containers, whether empty or containing study intervention. The participants must return unused study intervention to the study site.

Study intervention must be handled in strict accordance with the protocol and the container label and must be stored at the study site in a limited-access area or in a locked cabinet under appropriate environmental conditions. Unused study intervention and study intervention returned by the participant must be available for verification by the sponsor's study site monitor during on-site monitoring visits. The return to the sponsor of unused study intervention or used returned study intervention for destruction will be documented on the study intervention return form. When the study site is an authorized destruction unit and study intervention supplies are destroyed on-site, this must also be documented on the study intervention return form.

Study intervention should be dispensed under the supervision of the investigator or a qualified member of the study-site personnel, or by a hospital/clinic pharmacist. Study intervention will be supplied only to participants participating in the study. Returned study intervention must not be dispensed again, even to the same participant. Whenever a participant brings his or her study intervention to the study site for pill count, this is not seen as a return of supplies. Study intervention may not be relabeled or reassigned for use by other participants. The investigator agrees neither to dispense the study intervention from, nor store it at, any site other than the study sites agreed upon with the sponsor. Further guidance and information for the final disposition of unused study interventions are provided in the pharmacy manual.

### **6.3. Measures to Minimize Bias: Randomization and Blinding**

It is an open-label study; however, participants will be randomly assigned to 1 of 2 treatment groups based on a computer-generated randomization schedule prepared before the study. The randomization will be balanced by using randomly permuted blocks and will be stratified by country.

#### **Blinding**

As this is an open-label study, blinding procedures are not applicable. However, the microbiological results from Week 2 to Week 24 will be blinded to the investigators, site staffs and participants until the completion of the other assessments at Week 24 by the investigators. In order to maintain the blind, the investigator should not perform microbiological tests for acid-fast

bacillus at the study site after Day 1 until completion of the assessments other than microbiological assessments at the Week 24 except in emergency situations related to subject safety or chemotherapy. In case the investigators need to know the microbiological result to decide if participants should be switched to an individualized treatment regimen or continue the study treatment regimen, due to clinical worsening, the investigators can access the microbiological result from the central laboratory (for the detailed procedure, refer to the Procedure for Confirmation and Reporting of Results of Blinded Sputum Culture Including Collection of Samples for Microbiology Test). Sponsor except for specific personnel listed below must keep the blinding of all the microbiological assessment after Week 2 until unblinding takes place for the primary analysis.

In addition, sponsor personnel involved in monitoring of the study sites and personnel involved in management operation of the central laboratory etc. are excluded from maintenance of blinding for microbiology assessments, taking into account that sponsor needs to confirm that investigators and etc. comply with the protocol and the decision to switch to individualized treatment regimen and the optional cohort is made based on the appropriate process. Details will be provided in the statistical analysis plan (SAP).

The interim (futility) analysis is detailed in Section [9.5, Interim Analysis](#).

#### **6.4. Study Intervention Compliance**

[Table 3](#) provides instructions for when BDQ doses are missed or interrupted. Bedaquiline in the optional cohort will be administered according to Group A regimen. Interruption or missing dose of comparator or combination drug will be managed by investigators based on local practice and labeling.

**Table 3: BDQ Missed Dose and Interruption Instructions**

BDQ Missed Dose		BDQ Interruption	
Loading Phase (Weeks 1-2)		Loading Phase (Weeks 1-2)	
Participant notices missed dose within 12 hours of planned intake time	Participant notices missed dose 12 hours or later after planned intake time	BDQ interruption $\leq 14$ days	BDQ interruption $> 14$ days
⇓	⇓	⇓	⇓
Take missed dose and then resume dosing schedule	Do not take missed dose and resume dosing schedule	Continue dosing from last dose taken to complete total doses required in Loading Phase (previous doses taken into account)	Restart from beginning of Loading Phase to complete total doses required in Loading Phase (previous doses not taken into account)
		More than 1 interruption is not allowed (considered as treatment failures, 1 interruption is acceptable) Restarting is not permitted after interruptions of $> 30$ days (considered as treatment failures)	
Maintenance Phase (Weeks 3-48)		Maintenance Phase (Weeks 3-48)	
Participant notices missed dose in same dosing week of missed dose	Participant notices missed dose after dosing week of missed dose	BDQ interruption $\leq 14$ days	BDQ interruption between 15 to 30 days
⇓	⇓	⇓	⇓
Take missed dose as soon as possible and then resume dosing schedule	Do not take missed dose and resume dosing schedule	Dosing can be resumed after interruptions of up to 30 days. All interruptions must be reported to the sponsor within 3 working days of the study site becoming aware More than 1 interruption of 15 to 30 days is not allowed (considered as treatment failures, 1 interruption is acceptable) Restarting is not permitted after interruptions of $> 30$ days (considered as treatment failures)	

Note: BDQ in the optional cohort will be administered according to Group A regimen.

Study intervention compliance will be assessed by counting tablets and/or capsules returned and using participant diary during the site visits and documented in the source documents. The use of study intervention captured in participant diary will be recorded in the eCRF.

Combination drug compliance will be assessed by participant diary during the site visits and documented in the source documents. The use of combination drug captured in participant diary will be recorded in the eCRF.

## 6.5. Dose Modification

Any dose/dosage adjustment as described in Section 6.1, [Study Interventions Administered](#), should be overseen by medically-qualified study-site personnel (principal or subinvestigator unless an immediate safety risk appears to be present).

In case a dose reduction is necessary, the study drug will be administered per Section 6.1.

## 6.6. Continued Access to Study Intervention After the End of the Study

Participants will be instructed that study intervention will not be made available to them after they have completed/discontinued study intervention and that they should return to their primary physician to determine standard of care.

## 6.7. Treatment of Overdose

There is no experience with the treatment of acute overdose with BDQ.

For this study, any dose of BDQ greater than 400 mg within a 24-hour time period (-12 hour) from first day to 14 days after the first dose and 200 mg within a 72-hour time period (-24 hour) from 15 days will be considered an overdose. The sponsor does not recommend specific intervention for an overdose. Removal of unabsorbed BDQ may be achieved by gastric lavage or aided by the administration of activated charcoal. Since BDQ is highly protein-bound, dialysis is not likely to significantly remove BDQ from plasma.

Refer to the local package insert of the comparator rifamycin (RFP or RBT) for advice on treatment of overdose.

In the event of an overdose, the investigator or treating physician should:

- Contact the Medical Monitor immediately.
- Evaluate the participant to determine, in consultation with Medical Monitor, whether study intervention should be interrupted or dose should be reduced.
- Closely monitor the participant for AE/SAE and laboratory abnormalities. General measures to support basic vital functions including monitoring of vital signs and ECG (QT interval) should be taken in case of deliberate or accidental overdose.
- Obtain a plasma sample for PK analysis within 3 days from the date of the last dose of study intervention if requested by the Medical Monitor (determined on a case-by-case basis).
- Document the quantity of the excess dose as well as the duration of the overdosing in the eCRF.

Decisions regarding dose interruptions or modifications will be made by the investigator in consultation with the Medical Monitor based on the clinical evaluation of the participant.

## 6.8. Concomitant Therapy

Concomitant therapies administered after signing informed consent (70 days before first dose of study intervention, including the extension period if screening period is extended) and prestudy therapies for pulmonary MAC disease administered prior to signing informed consent must be recorded at screening.

Concomitant therapies must be recorded throughout the study from signing of the ICF up to the last study visit. Concomitant therapies should also be recorded beyond the last follow-up visit only in conjunction with new or worsening AEs and SAEs that meet the criteria outlined in Serious

Adverse Events in Section 8.3.1, Time Period and Frequency for Collecting Adverse Event and Serious Adverse Event Information.

All therapies (prescription or over-the-counter medications, including vaccines, vitamins, herbal supplements; nonpharmacologic therapies such as electrical stimulation, acupuncture, special diets, exercise regimens, or other specific categories of interest) different from the study intervention must be recorded in the Concomitant Therapy Section of the eCRF. Recorded information will include a description of the type of therapy, duration of use, dosing regimen, route of administration, and indication. For any concomitant therapy given as a treatment for a new condition or worsening of an existing condition, the condition must be documented in the Adverse Event Section of the eCRF. Modification of an effective preexisting therapy should not be made for the explicit purpose of entering a participant into the study.

It is important to record the use of biotin because of its potential to affect certain laboratory assays when high levels of biotin are present in serum/plasma samples, leading to incorrect test results for certain laboratory parameters. All prior and concomitant treatment with MAC-LD drugs will be recorded. For participants who were previously diagnosed with MAC-LD and are being treated or will start treatment at screening, the start date and details of their treatment regimen must be recorded. Participants who are taking rifamycin before start of the study intervention will be required to discontinue rifamycin to allow for a minimum 14-day washout period (to avoid DDIs between rifamycins and BDQ). Participants who are transferred to the optional cohort will be required to discontinue rifamycin to allow for a minimum 14-day washout period before start of the BDQ-containing regimen.

If contraindicated medication(s) listed in each package insert of comparator/combination drugs (RFP, RBT, CAM, or EB) are received during screening, the contraindicated medication(s) are prohibited from 7 days prior to Day 1 up to the last dose of the medications including study intervention.

Antibacterial drugs, such as fluoroquinolones, linezolid that may be effective for MAC-LD other than the specified concomitant medications are prohibited during the study treatment period.

When injectable aminoglycoside is used as part of an individualized treatment regimen, injectable KM is prohibited throughout the study period, because it is not approved for the treatment of NTM-LD. Injectable SM, injectable or inhalation suspension of AMK is acceptable as part of an individualized treatment regimen. The use of injectable SM, injectable or inhalation suspension of AMK for any purposes other than as part of an individualized treatment regimen is prohibited.

The following medications are prohibited from 2 weeks prior to Day 1 up to the last dose of study intervention (see note):

- systemic use of moderate and strong CYP3A4 inhibitors (eg, azole antifungals: ketoconazole, fluconazole, voriconazole, itraconazole; ketolides such as telithromycin; and macrolide antibiotics [except CAM]) for more than 2 weeks.

- systemic use of strong CYP3A4 inducers (eg, phenytoin, carbamazepine, phenobarbital, St. John's wort [*Hypericum perforatum*], and systemic, multiple dosing of dexamethasone), except rifamycins for those randomized to the rifamycin-containing regimen.

**NOTE:** For participants receiving BDQ, the above prohibited medication can be (re-)started 1 month after stopping BDQ.

**NOTE:** The examples of potent CYP3A4 inhibitors and inducers do not form a complete list. The investigator should consult the prescribing information for study interventions and combination drugs (CAM and EB) and, if necessary, contact the appropriate sponsor representative.

The following medications are prohibited because of their potential for QTc prolongation. These medications are not allowed from 7 days prior to Day 1 up to the last dose of study interventions and combination drugs (CAM and EB) (including individualized treatment regimens):

- antiarrhythmics Class IA (eg, quinidine, hydroquinidine, disopyramide)
- antiarrhythmics Class III (eg, amiodarone, sotalol, dofetilide, ibutilide)
- neuroleptics: phenothiazines thioridazine, haloperidol, chlorpromazine, trifluoperazine, pericycline, prochlorperazine, fluphenazine, sertindole, and pimozide
- quinolone antimalarials (eg, chloroquine and quinacrine)
- moxifloxacin (prohibited from the initiation date of BDQ treatment up to 1 month after the last dose of BDQ)
- antimicrobials: erythromycin intravenous (IV), pentamidine, delamanid
- tricyclic antidepressants, including amitriptyline, doxepin, desipramine, imipramine, and clomipramine
- prokinetic cisapride
- nonsedating antihistamines: astemizole, terfenadine, and mizolastine
- clofazimine (increased QT prolongation is reported in co-administration with BDQ)

**NOTE:** The above list of drugs with known risk of QT prolongation is based on drugs that may be commonly used during the treatment of NTM-LD. The investigator should consult current publicly available drug information to identify other drugs with potential QT prolongation. The list of potential QT prolonging drugs is long and subject to change. Clinical interpretation of known and potential additive risks is required.

The following medications are prohibited because of their potential for muscle damage (myopathy) from 7 days prior to Day 1 up to the last dose of study interventions and combination drugs (CAM and EB) (including individualized treatment regimens) (see note):

- 3-hydroxy-3-methylglutaryl-coenzyme A reductase inhibitors (statins)
- griseofulvin

**NOTE:** All prohibited medications with a risk for muscle damage (myopathy) can be (re-)started 1 month after BDQ discontinuation.

Hepatotoxic medications should be used with caution, especially during the treatment period in participants with signs of hepatotoxicity (eg, participants with transaminase elevations). Alternative medications should be used if possible.

For participants who change their treatment regimen, latest package inserts should be consulted for contraindicated medication(s) or medication(s) that is not recommended for concomitant use.

The sponsor must be notified in advance (or as soon as possible thereafter) of any instances in which prohibited therapies are administered.

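### Protocol Section 6.8 ends the ban on nine of ten QTc-list entries at the last dose of study drug, CAM and EB, without the 1-month wait after bedaquiline that it sets for its other lists

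*Protocol*

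**What the plan says.** Protocol Section 6.8 (Concomitant Therapy) has three lists of drugs barred because of an interaction or an additive toxicity.

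- **QTc list.** These drugs are "not allowed from 7 days prior to Day 1 up to the last dose of study interventions and combination drugs (CAM and EB". The header does not point to a note on restarting. One entry has its own dates: "moxifloxacin (prohibited from the initiation date of BDQ treatment up to 1 month after the last dose of BDQ". Another gives its reason but no dates: "clofazimine (increased QT prolongation is reported in co-administration with BDQ". The note under the list says "Clinical interpretation of known and potential additive risks is required" and gives no restart time.
- **Myopathy list.** The header has the same end point but adds a pointer: "up to the last dose of study interventions and combination drugs (CAM and EB) (including individualized treatment regimens) (see note". The note reads: "All prohibited medications with a risk for muscle damage (myopathy) can be (re-)started 1 month after BDQ discontinuation".
- **CYP3A4 list.** The ban runs to the last dose of study intervention, again with a pointer to a note: "For participants receiving BDQ, the above prohibited medication can be (re-)started 1 month after stopping BDQ".

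For participants whose regimen changes, the section adds that "latest package inserts should be consulted for contraindicated medication(s". No other section sets a restart interval for the QTc list.

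**The concern.** QT prolongation from BDQ and/or CAM is a named risk in Protocol Section 2.3.1. BDQ leaves the body slowly, and the protocol acts on this elsewhere: under Section 8.2.3, unresolved QTcF prolongation keeps weekly ECGs going until 4 weeks after the last BDQ dose, because of the long half-life. A list meant to prevent additive QT effects would be expected to respect the same period, as the myopathy and CYP3A4 lists do.

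As written, a site reading Section 6.8 literally would hold back a statin for a month after BDQ but would find no stated wait for a Class III antiarrhythmic or a tricyclic. What is at stake is clear instruction to sites on a cardiac risk. The primary endpoint, the sample size and the analysis are not touched.

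**Working it through.** The plan gives no figure to reproduce here. The check is a count and a side-by-side reading, all from the Protocol.

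**1. Count of the QTc list (Section 6.8).** Class IA antiarrhythmics; Class III antiarrhythmics; neuroleptics; quinolone antimalarials; moxifloxacin; antimicrobials (IV erythromycin, pentamidine, delamanid); tricyclics; cisapride; nonsedating antihistamines; clofazimine. That is 10 entries. With their own post-BDQ limit: 1 (moxifloxacin). Without: 10 − 1 = 9.

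One qualification: IV erythromycin is a macrolide. Macrolides other than CAM, used systemically for more than 2 weeks, fall under the CYP3A4 list and so under its 1-month note. This covers one drug within one entry, and only for longer use.

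**2. The three lists compared.**

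| List | Ban ends at last dose of | Header points to a restart note | Wait after BDQ |
|---|---|---|---|
| CYP3A4 | study intervention | yes | 1 month |
| Myopathy | study interventions, CAM and EB | yes | 1 month |
| QTc | study interventions, CAM and EB | no | moxifloxacin 1 month; other 9 entries none of their own |

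The like-for-like comparison is with the myopathy list, which has the same end point and differs only in having a restart note.

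**3. When the gap opens.** The QTc ban lasts as long as CAM or EB continues, so nothing is missing while either is taken. The gap opens only when both stop together with BDQ:
- Group A converters after Week 48, who enter 12 weeks free of MAC-LD treatment (Section 4.1). They remain in the study.
- Early discontinuers, who are not automatically withdrawn (Section 7.2). Some may remain in the study.
- Optional-cohort completers at OPW48 and Group A non-converters at Week 48. These leave the study, and Section 6.6 sends participants back to their primary physician.

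**4. Drug remaining.** Section 2.2 reports, from Phase 2, that mean BDQ and M2 concentrations fell by about 40% in the 4 weeks after stopping: 100% − 40% = about 60% remaining. The same section gives a terminal half-life of 5.5 months for BDQ. The terminal phase alone would leave 0.5^(1/5.5) = 0.88 after 1 month, so the reported 60% already includes the faster early decline.

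**5. What the safeguards cover.** Converters have ECGs at Weeks 52, 56 and 60 (Section 1.3). The first falls nominally 365 − 337 = 28 days after the Week 48 visit, at about the end of the month in question. Weekly ECGs apply only to participants with QTcF prolongation. ECGs detect prolongation but do not say when a listed drug may be started. The clinical-interpretation note and the package-insert advice set no interval either.

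**6. After the fix.** All 10 entries would carry a post-BDQ wait, against 1 of 10 now, and the three lists would agree.

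**The case against.** The case against has several parts, and some of them stand.

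- **Reach.** Converters must stay free of MAC-LD treatment, and a participant needing a regimen outside those in Section 6.8.1 is to be discontinued. A reader might infer that clofazimine could be started for MAC-LD within the study the day after BDQ. The documents do not support that: it would arise essentially only after exit, where a protocol note is advice. What remains in the study is mainly a converter, or an early discontinuer who stays, newly starting an antiarrhythmic, neuroleptic, tricyclic or similar drug. Exclusion criteria 7 and 8 make this uncommon. This stands.
- **Clinical judgement.** The end of a listed ban does not clear a drug for use, and the note under the list asks investigators to weigh additive risk. This stands against any reading that the protocol approves next-day use. It does not explain why moxifloxacin and the other two lists need a fixed interval and the rest of this list does not.
- **Intent.** Moxifloxacin has its own start date as well as its own end date, so its rule may be drug-specific, and the other two notes serve different risks. A reader might infer a proven drafting oversight. The documents show an unexplained inconsistency, not its cause.
- **Size of the effect.** A reader might try to adapt the 60% to this regimen using the 37% reduction in BDQ clearance with CAM (Section 4.3). The documents do not support this: when CAM stops too, clearance should move back towards its level without CAM, and the decline is multiphasic. The added QT effect cannot be derived either. The reported mean QTcF increase of 10-15 ms (Section 2.2) is with BDQ treatment, not for a combination started after it.
- **Benefit and timing.** With about 60% remaining at 4 weeks, 1 month is not shown to be a QT safety threshold. SAP version 4 (31 January 2025) already describes all subjects as compliers, which suggests treatment was well advanced and few could still benefit. Both points limit the gain, but neither makes the text consistent.

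**Conclusion.** The point holds as a safety-wording inconsistency of limited reach. Nine of 10 QTc-list entries have no post-BDQ wait of their own, with the partial exception of longer IV erythromycin use. The tenth entry and both other lists have 1 month. When CAM and EB stop with BDQ, the stated ban ends while, on the protocol's Phase 2 data, about 60% of BDQ and M2 would remain 4 weeks later.

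This rests on two assumptions: that the Phase 2 decline is a fair guide to slow elimination here, though not a prediction for this regimen, and that sites follow the list as written. The number of participants who would start a listed drug in that month is not given and is probably small. Participants stopped for QTcF prolongation have weekly ECGs but equally no interval if CAM and EB stop too. No estimand, analysis or efficacy result changes.

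**What to change.** Add a pointer to a note in the QTc header, as in the myopathy list, and add this note: for participants who received BDQ, listed medications may be (re-)started 1 month after stopping BDQ, or after the last dose of CAM/EB if that is later, except for medically necessary use after contact with the sponsor and with ECG monitoring. Give the same advice at exit to participants who leave the study, including any who may go on to clofazimine.

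The 1 month is the sponsor's own interval, reused for consistency, and should not be presented as a derived QT safety threshold.

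The cost is a slightly longer restriction after BDQ, eased by the medical-need exception, and a protocol amendment. Because the change is not purely administrative, Section 10.3.1 requires ethics committee approval, so it is best bundled with the next amendment. The SAP needs no change.
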